4.2. Scientific Rationale for Study Design

Study GPIM is designed to determine the comparative benefits and risks of QW tirzepatide (5 mg, 10 mg, or 15 mg) versus placebo in participants with T2DM who have inadequate glycemic control on stable doses of insulin glargine alone or in combination with metformin with or without SGLT-2i.

The planned treatment duration of 40 weeks is considered appropriate to assess the full effects and benefit/risk of each maintenance dose of tirzepatide on both glycemic control and body weight based on the experience of the international multicenter Phase 3 Study SURPASS-5 (GPGI). Moreover, the duration of the study is considered sufficient and appropriate for participants to optimize dosing of insulin glargine in the placebo group for comparison with the tirzepatide treatment groups with respect to change in HbA1c.

The parallel-group design for treatment comparison was chosen to avoid any interaction between treatments that may interfere with the interpretation of the study outcome. To minimize the potential confounding effect of changes to concomitant medications, participants will be permitted to use concomitant medications that they require during the study. Medications that may interfere with the assessment of efficacy and safety characteristics of the study treatments will not be allowed (see Section 6.8).

4.3. Justification for Dose

Tirzepatide doses of 5 mg, 10 mg, and 15 mg administered subcutaneously QW will be evaluated in this study.

The dose selection of tirzepatide and associated escalation schemes in this study are based on the findings in 5 completed global Phase 3 studies (SURPASS clinical program, including GPGK, GPGL, GPGH, GPGM, and GPGI) in participants with T2DM (Del Prato et al. 2021; Frías et al. 2021; Ludvik et al. 2021; Rosenstock et al. 2021; Dahl et al. 2022), as well as 1 completed Phase 3 study (SURPASS-AP-Combo [GPHO]) which is the first registration trial of tirzepatide that enrolled a majority of Chinese participants with T2DM. The starting dose of tirzepatide is 2.5 mg QW, which is to be escalated at 4-week intervals at 2.5 mg increments (2.5 to 5 to 7.5 to 10 to 12.5 to 15 mg) until the participant reaches 5, 10 or 15 mg. Such approach should permit the development of tolerance to GI events and is expected to minimize GI AEs consistent with the completed 6 Phase 3 T2DM studies.

Tirzepatide demonstrated superior efficacy for glycemic control and body weight reduction as well as an improvement in different factors associated with an increased risk of longer-term cardiometabolic complications in participants with T2DM. (Del Prato et al. 2021; Frías et al. 2021; Ludvik et al. 2021; Rosenstock et al. 2021; Dahl et al. 2022). Similar to the GLP-1 RA class, most of the tirzepatide AEs were dose dependent and GI related, consisting mainly of nausea, vomiting, and diarrhea. In general, these events were mild or moderate in severity, with few severe episodes, and transient (Del Prato et al. 2021; Frías et al. 2021; Ludvik et al. 2021; Rosenstock et al. 2021; Dahl et al. 2022).

Tirzepatide doses were selected based principally on the following criteria:

- each dose provides clinically meaningful weight loss relative to placebo, and
- safety and tolerability were supported by Phase 3 T2DM results.

4.4. End of Study Definition

End of the study is the date of the last visit or last scheduled procedure shown in the SoA (Section 1.3) for the last participant.

5. Study Population

Prospective approval of protocol deviations to recruitment and enrollment criteria, also known as protocol waivers or exemptions, is not permitted.

5.1. Inclusion Criteria

Participants are eligible to be included in the study only if they meet all of the following criteria at screening:

Type of Participant and Disease Characteristics

- [1] Have been diagnosed with T2DM based on the World Health Organization classification (Section 10.6)

Participant Characteristics

- [2] Have HbA1c $\geq 7.0\%$ (53 mmol/mol) to $\leq 11\%$ (97 mmol/mol), as determined by the central laboratory at Visit 1
- [3] Have been treated with insulin glargine (U100) once daily alone, or in combination with metformin with or without SGLT-2i ≥ 90 days prior to Visit 1
- [4] Doses of once daily insulin glargine and OAMs (if used) must be stable during the 90-day period prior to Visit 1
 - All insulin glargine doses must be ≥ 0.2 U/kg/day or ≥ 15 U/day during the 90-day period prior to Visit 1. Insulin glargine dose is considered stable when all doses during this period are within the range defined by $\pm 20\%$ of the most commonly used insulin dose during this same period.
 - Doses of metformin (if used) are considered stable when dose and formulation are unchanged during the same period, and the doses must be ≥ 1000 mg/day and no more than the maximum approved dose per country specific label.
 - Doses of SGLT-2i (if used) are considered stable when participants are on the same SGLT-2i and the dose is unchanged during the same period, and the doses must be at least the recommended starting dose and no more than the maximum approved dose per country specific label.
- [5] Require further insulin glargine dose increase at Visit 3 per the TTT algorithm based on the SMBG data: $\geq 50\%$ FBG values > 5.6 mmol/L collected during the week prior to Visit 3.
- [6] Are of stable weight ($\pm 5\%$) during the 90-day period prior to Visit 1 and agree to not initiate a diet and/or exercise program during the study with the intent of reducing body weight other than the lifestyle and dietary measures for diabetes treatment.
- [7] Have body mass index (BMI) ≥ 23 kg/m² at Visit 1
- [8] Are ≥ 18 years old or of an acceptable age to provide informed consent according to local regulations, whichever is older

Males and females may participate in this trial.

Female participants must not be pregnant, intending to be pregnant, breastfeeding, or intending to breastfeed.

Contraceptive use by participants should be consistent with local regulations regarding the methods of contraception for those participating in clinical studies. For the definitions and the contraception requirements of this protocol, see Appendix 4 (Section 10.4).

[9] In the investigator's opinion, are well-motivated, capable, and willing to:

- (a) perform fingerstick BG monitoring, including scheduled BG profiles with up to 7 measurements in 1 day
- (b) learn how to self-inject study drugs as required for this protocol (visually impaired persons who are not able to perform the injections must have the assistance of a sighted individual trained to inject the study drug; persons with physical limitations who are not able to perform the injections must have the assistance of an individual trained to inject the study drug)
- (c) are willing and able to inject study drugs
- (d) maintain a study diary, as required for this protocol
- (e) have a sufficient understanding of one of the provided languages of the country such that they will be able to complete the participant questionnaires

Informed Consent

[10] Have given written informed consent to participate in this study in accordance with local regulations and the ethical review board (ERB) governing the study site

5.2. Exclusion Criteria

Participants will be excluded from the study if they meet any of the following criteria at Visit 1 (screening), or when indicated below for specific criteria, at Visit 3 (baseline) or at any time during the screening and lead-in periods (Visits 1-3):

Medical Conditions

[11] Have type 1 diabetes mellitus (T1DM)

[12] Have a history of chronic or acute pancreatitis prior to Visit 1 or between Visit 1 and Visit 3

[13] Have history of:

- proliferative diabetic retinopathy
- or
- diabetic macular edema
- or
- nonproliferative diabetic retinopathy that requires acute treatment

(a dilated fundoscopic examination performed by an ophthalmologist or optometrist between Visit 2 and Visit 3 is required to confirm eligibility)

- [14] Have a history of severe hypoglycemia and/or hypoglycemia unawareness within the 6 months prior to Visit 1
- [15] Have a history of diabetic ketoacidosis or hyperosmolar state/coma within the 6 months prior to Visit 1
- [16] Have a known clinically significant gastric emptying abnormality (for example, severe diabetic gastroparesis or gastric outlet obstruction), have undergone or plan to have during the course of the study: a gastric bypass (bariatric) surgery or restrictive bariatric surgery (for example, Lap-Band[®]), or chronically take drugs that directly affect GI motility
- [17] Have any of the following cardiovascular (CV) conditions within 2 months prior to Visit 1 or between Visit 1 and Visit 3: acute myocardial infarction, or cerebrovascular accident (stroke) or hospitalization due to congestive heart failure (CHF)
- [18] Have New York Heart Association Functional Classification III and IV CHF within 2 months prior to Visit 1 or between Visit 1 and Visit 3
- [19] Have acute or chronic hepatitis, signs and symptoms of any other liver disease other than nonalcoholic fatty liver disease (NAFLD), or alanine aminotransferase (ALT) level >3.0 times the upper limit of normal (ULN), as determined by the central laboratory at Visit 1; participants with NAFLD are eligible for participation in this trial only if their ALT level is ≤ 3.0 times ULN
- [20] Have an estimated glomerular filtration rate (eGFR) <30 mL/min/1.73 m², calculated by Chronic Kidney Disease-Epidemiology (CKD-EPI) as determined by central laboratory at Visit 1; for participants on metformin, eGFR (CKD-EPI) <45 mL/min/1.73 m² as determined by the central laboratory at Visit 1; for participants on metformin and SGLT-2i, eGFR (CKD-EPI) either <45 mL/min/1.73 m² or lower than the threshold defined in SGLT-2i label, as determined by central laboratory at Visit 1.
- [21] Have evidence of a significant, uncontrolled endocrine abnormality (for example, thyrotoxicosis or adrenal crises), in the opinion of the investigator
- [22] Have family or personal history of medullary thyroid carcinoma (MTC) or multiple endocrine neoplasia syndrome type 2
- [23] Have a serum calcitonin level of ≥ 35 ng/L, as determined by central laboratory at Visit 1
- [24] Known or suspected hypersensitivity to trial product(s) or related products
- [25] Have evidence of a significant, active autoimmune abnormality (for example, lupus or rheumatoid arthritis) that, in the opinion of the investigator, is likely to require concurrent treatment with systemic glucocorticoids in the next 12 months

- [26] Have had a transplanted organ (corneal transplants [keratoplasty] allowed) or awaiting an organ transplant
- [27] Have a history of an active or untreated malignancy or are in remission from a clinically significant malignancy for less than 5 years. Exceptions for this criterion are
 - basal or squamous cell skin cancer
 - *in situ* carcinomas of the cervix, and
 - *in situ* or grade 1 (for example, Gleason 6 or lower) prostate cancer
- [28] Have a history of any other condition (such as known drug, alcohol abuse, or psychiatric disorder) that, in the opinion of the investigator, may preclude the participant from following and completing the protocol
- [29] Males with hemoglobin <11.0 110 g/L and females with hemoglobin <10.0 100 g/L; or any hematological condition that may interfere with HbA1c measurement (for example, hemolytic anemias and sickle cell disease)

Prior/Concomitant Therapy

- [30] Treatment with any glucose-lowering agent(s) other than stated in the inclusion criteria [3] in a period of 90 days prior to Visit 1 and between Visit 1 and Visit 3
 - Note:** Short-term treatment with a nonstudy insulin for up to 14 days is allowed for certain clinical situations.
- Examples:** Elective surgery, during hospitalization or hyperosmolar states
- [31] Have been treated with prescription drugs that promote weight loss (for example, Wegovy® [semaglutide 2.4 mg], Saxenda [liraglutide 3.0 mg], Xenical® [orlistat], Meridia® [sibutramine], Acutrim® [phenylpropanolamine], Sanorex® [mazindol], Apidex® [phentermine], BELVIQ® [lorcaserin], Qsymia™ [phentermine/topiramate combination], Contrave® [naltrexone/bupropion], or similar other body weight loss medications including over-the-counter (OTC) medications [for example, alli®]) within 90 days prior to Visit 1 and/or between study entry (Visit 1) and randomization (Visit 3)
- [32] Are receiving chronic (>14 days) systemic glucocorticoid therapy (excluding topical, intraocular, intranasal, intra-articular or inhaled preparations) or have received such therapy within 1 month of Visit 1 or between Visits 1 and 3

Prior/Concurrent Clinical Trial Experience

- [33] Are currently enrolled in any other clinical study involving an investigational product or any other type of medical research judged not to be scientifically or medically compatible with this study
- [34] Have participated, within the last 30 days in a clinical study involving an investigational product. If the previous investigational product has a long half-life, 5 half-lives or 30 days (whichever is longer) should have passed

- [35] Have previously completed or withdrawn from this study or any other study investigating tirzepatide

Other Exclusions

- [36] Are investigator site personnel directly affiliated with this study and/or their immediate families. Immediate family is defined as a spouse, parent, child, or sibling, whether biological or legally adopted
- [37] Are Lilly employees
- [38] Are unwilling or unable to comply with the use of a paper diary to directly record data from the subject

5.3. Lifestyle Considerations

Per the SoA (Section 1.3), qualified medical personnel will provide diabetes management counseling, which will include instructions on diet and exercise and education about the signs, symptoms, and treatment of hypoglycemia, should it occur.

Participants should continue their usual exercise habits and generally follow a healthy meal plan (with consistent meal size and time of day) throughout the course of the study. Dietary counseling may be reviewed throughout the study, as needed. Per inclusion criterion [6] (Section 5.1), participants should not initiate during the study an organized diet and/or exercise weight reduction program other than the lifestyle and dietary measures for diabetes treatment.

Study participants should be instructed not to donate blood or blood products during the study.

5.4. Screen Failures

A screen failure occurs when a participant who consents to participate in the clinical study is not subsequently randomly assigned to study drug. A minimal set of screen failure information is required to ensure transparent reporting of screen failure participants to meet the Consolidated Standards of Reporting Trials (CONSORT) publishing requirements and to respond to queries from regulatory authorities. Minimal information includes demography, screen failure details, eligibility criteria, and any serious adverse event (SAE).

Individuals who do not meet the criteria for participation in this study (screen failure) must not be rescreened.

5.5. Criteria for Temporarily Delaying Enrollment/Randomization/Administration of Study Intervention of a Participant

Not applicable.

6. Study Intervention(s) and Concomitant Therapy

Study intervention is defined as the study drug (tirzepatide 3 doses or placebo) intended to be administered to a study participant according to the study protocol.

6.1. Study Intervention(s) Administered

Assignment to tirzepatide (3 doses) or placebo will occur at randomization. Beginning at randomization, all participants will receive study drug according to the randomized treatment group for the duration of the 40-week treatment period. Following randomization, the participant will inject the first dose of study drug/placebo at the study site. The date and time of all doses of study drug should be recorded on the eCRF.

This table lists the interventions used in this clinical study.

Group Name	Tirzepatide 5 mg	Tirzepatide 10 mg	Tirzepatide 15 mg	Placebo	Concomitant background insulin for all treatment arms
Intervention Name	Tirzepatide 5 mg	Tirzepatide 10 mg	Tirzepatide 15 mg	Placebo	Insulin Glargine U100
Dosage Level(s)	5 mg QW	10 mg QW	15 mg QW	NA	Titrated
Route of Administration	SC				
Frequency of Administration	QW				QD
Use	Experimental intervention			comparator	Concomitant background insulin
Sourcing	Provided centrally by the Sponsor and dispensed via IWRS				
Packaging and Labeling	Will be provided in autoinjectors (single-dose pens) and packaged in cartons to be dispensed. Clinical study materials will be labeled according to country regulatory requirements.				

Abbreviations: IWRS= interactive web-response system, QD= once daily, QW=once weekly, SC=subcutaneous.

[figure not shown]
6.1.1. Tirzepatide Dosing

The starting dose of tirzepatide will be 2.5 mg QW for 4 weeks, followed by an increase to 5 mg QW, for the duration of the study in the 5-mg group.

For the 10-mg group, the starting dose of tirzepatide will be 2.5 mg QW for 4 weeks, then the dose will be increased by 2.5 mg every 4 weeks (2.5 to 5 to 7.5 to 10 mg) until the 10-mg dose is reached and maintained for the duration of the study.

For the 15-mg group, the starting dose of tirzepatide will be 2.5 mg QW for 4 weeks, then the dose will be increased by 2.5 mg every 4 weeks (2.5 to 5 to 7.5 to 10 to 12.5 to 15 mg) until the 15-mg dose is reached and maintained for the duration of the study.

Figure GPIM.1 illustrates the tirzepatide dose escalation regimen.

Abbreviations: Met = metformin; QW = once weekly; SGLT-2i = sodium-glucose transport protein 2 inhibitor.

Figure GPIM.1. Tirzepatide Dose Escalation

There are no restrictions on the time of day each weekly dose of study drug is given, but it is advisable to administer the subcutaneous (SC) injections on the same day and same time each week. The actual date and time of all dose administrations will be recorded by the participant. If a dose of study drug is missed, the participant should take it as soon as possible unless it is within 72 hours of the next scheduled dose, in which case, that dose should be skipped and the next dose should be taken at the appropriate time. The day of weekly administration can be changed if necessary, as long as the last dose was administered 72 or more hours before.

All participants will inject study drug subcutaneously in the abdomen or thigh using the SDP; a caregiver may administer the injection in the participant's upper arm. A new SDP will be used for each injection. If study drug is to always be injected in the same body region, participants should be advised to use a different injection site each week.

6.1.2. Placebo Dosing

Participants randomized to the placebo group will inject matched placebo subcutaneously QW for the entire treatment period. This is a double-blind study, and therefore it will not be possible for investigators and participants to know which treatment they are receiving.

6.1.3. Insulin Glargine Dosing

Insulin glargine will be injected once daily, as a single SC injection, always at the same time of day, ideally at bedtime. Participants will be instructed to adjust insulin glargine doses to a target FBG of ≤ 5.6 mmol/L (100 mg/dL) according to the schedule below ([Table GPIM.1](#)). For this purpose, participants will be encouraged to measure their FBG each morning and to collect 4-point SMBG profiles at least once a week through the end of the treatment period (Visit 19 [Week 40]). The 4-point SMBG profile will consist of fasting, pre-midday meal, pre-evening meal, and bedtime measures. Participants will collect the 4-point SMBG profiles once weekly between Visit 2 and Visit 3, twice weekly from Visits 3-7 (Weeks 0-4) followed by once weekly for the remainder of the treatment period.

The decision to adjust insulin glargine doses will be based upon the median of the last 3 daily FBG (SMBG) values collected after the previous dose assessment. If only 2 values are available for assessment, then the average value will be calculated and used to adjust the dose. If only one value is available, the participant should contact the investigator site for instructions on adjusting insulin dose. In case of recorded hypoglycemic episodes any time during the period included in the assessment, the criteria provided as footnotes to [Table GPIM.1](#) should be followed.

Table GPIM.1. Treat-to-Target Algorithm

Median Fasting Blood Glucose ^a		Adjustment of Insulin Glargine Dose
mg/dL	mmol/L	
<79	<4.4	-2 units ^{b,c}
79 to 99	4.4 to 5.5	No adjustment
100 to 119	5.6 to 6.6	+(0-2) units (at the discretion of investigator)
120 to 139	6.7 to 7.7	+2 units
140 to 179	7.8 to 9.9	+4 units
≥ 180	≥ 10.0	+6 units

Abbreviations: SMBG = self-monitored blood glucose.

^a Based on the last 3 fasting glucose values (SMBG).

^b Dose should also be decreased by 2 units in the following situations:

- If ≥ 2 episodes of nonsevere hypoglycemia <3.9 mmol/L (<70 mg/dL) were recorded during the assessment period at any time during the day; and/or
- If ≥ 1 episode that met the criteria for severe hypoglycemia (events requiring assistance of a third person to administer therapy) or was associated with SMBG value <3.0 mmol/L (<54 mg/dL) was recorded during the assessment period.

^c If only 1 hypoglycemic episode with SMBG value ≥ 3.0 mmol/L (≥ 54 mg/dL) and <3.9 mmol/L (<70 mg/dL) was recorded, insulin dose should not be changed.

Source: [Davies et al. 2005](#); [Ran et al. 2020](#); [Ji et al. 2018](#).

The site personnel will instruct the participant, with the participant insulin dose adjustment from the participant diary and study-specific training materials provided to the study sites, when and how to assess whether an insulin dose adjustment is needed using the algorithm. The investigator or his or her designee is responsible to ensure that the insulin dose titration regimen used by study participants follows the same requirements defined in the TTT plan throughout the study. The participant is responsible for completing the insulin dose assessments and making the required dose adjustments (self-adjustment). Assessment of insulin doses per the TTT algorithm and administered insulin doses will be recorded by the participant in study period-specific diaries. Participants should be instructed to contact the study site if they are unable to decide on the appropriate dose adjustment at any time during the trial. Site personnel will verify at each office or telephone visit that the assessment(s) has been made and that the insulin adjustment was appropriate. If needed, they will propose further adjustments based upon their review of data collected since the previous visit. If assessments were not made or the algorithm was not correctly followed, participants will receive additional training and instructions.

During the lead-in period (Visits 2 and 3 [randomization]), insulin doses should be adjusted only when needed to protect the safety of participants (occurrence of hypoglycemia or severe hyperglycemia). If these events occur, the insulin dose should be adjusted according to the TTT algorithm ([Table GPIM.1](#)). See Section [4.1.1](#) for more details. Insulin dose assessments during this period will occur once per week.

During the treatment period, office visits will occur weekly or every other week during the first 16 weeks, and thereafter every 4 to 8 weeks to enable the site to properly monitor participants' usage of the TTT algorithm. After randomization, during the 4-week stabilization period, the insulin glargine dose will remain unchanged if the participant's HbA1c at randomization (baseline, Visit 3) is >8.0%. For participants with baseline HbA1c ≤8.0%, the insulin glargine dose will be decreased by 20% immediately (within 7 days) after randomization and will then remain unchanged during the stabilization period. Insulin doses should be adjusted per TTT algorithm only when needed to protect the safety of participants (occurrence of hypoglycemia or severe hyperglycemia). If these events occur, the insulin dose should be adjusted according to the TTT algorithm ([Table GPIM.1](#)). See Section [4.1.1](#) for more details.

Participants will be requested to perform insulin dose assessments twice per week during the stabilization period for safety purposes. Following stabilization, participants will be treated for an additional 36 weeks, and they will be required to assess their insulin glargine dose once weekly, using the FBG values for that week. During this period, the insulin dose will be adjusted per the TTT algorithm as described in Section [4.1.1](#) with no restriction.

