6.5.2. Background Antihyperglycemic Medications

1. If increased risk of hypoglycemia during the period between 2 insulin dose assessments is judged to be related to the treatment regimen, the following changes should be made:
 - Decrease the insulin glargine dose by 2 U, per the TTT algorithm, in the following cases:
 - If ≥ 2 episodes of nonsevere hypoglycemia (<3.9 mmol/L [<70 mg/dL]) were recorded at any time during the day for the assessment period; and/or
 - If ≥ 1 episode that met the criteria for severe hypoglycemia (events requiring assistance to administer therapy) or was associated with SMBG value <3.0 mmol/L (<54 mg/dL) was recorded during the assessment period; and/or
 - If the median FPG value for the assessment period is <4.4 mmol/L (<79 mg/dL).
 - In the case of repeated hypoglycemic events, even with a very low glargine dose and despite glargine dose decreases per the TTT algorithm, administration of insulin glargine may be temporarily or permanently discontinued.
 - If increased risk of hypoglycemia persists despite discontinuation of insulin glargine, then dose reduction or discontinuation of OAMs (for participants who are taking) should be considered.
2. In certain situations, short-term discontinuation will be allowed in line with the product(s) labeling (for example, for metformin: severe dehydration, elective surgery, or need for radiologic examination involving intravenous injection of iodinated contrast dye; for SGLT-2i: ketoacidosis or clinical condition known to predispose to ketoacidosis [eg, prolonged fasting due to acute illness or surgery]). Once the situation that led to temporary discontinuation of the drug resolved, treatment should be restarted at investigator discretion.

3. If a participant develops contraindications to metformin or SGLT-2i (if used), such that the use of the drug is contraindicated according to the country specific label (eg, eGFR [CKD-EPI] lower than the threshold defined in country specific label), the drug should be discontinued; in this case, the insulin glargine dose may need to be further adjusted.

A participant will be considered noncompliant with the protocol (protocol deviation) if he or she changes the dose, or discontinues metformin or SGLT-2i (if used) for reasons other than those described here. Doses of background OAMs could be increased as rescue therapy for severe, persistent hyperglycemia, at the discretion of investigators (see Section [8.3.4.2](#) for details).

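### Read literally, footnote c of the insulin titration table withholds the 2-unit reduction from a participant with median fasting glucose <4.4 mmol/L and one Level 1 episode; the table row and Section 6.5.2 point the other way, and the footnote's scope is not stated

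*Protocol*

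**What the plan says.** Protocol Section 6.1.3 bases each glargine adjustment on the median of the last three fasting self-monitored values. Table GPIM.1 gives -2 units for a median <4.4 mmol/L, and this is the only cell marked with footnotes b and c.

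- Footnote b: "Dose should also be decreased by 2 units in the following situations". It then lists two or more nonsevere episodes <3.9 mmol/L, or at least one that was severe or <3.0 mmol/L.
- Footnote c begins "If only 1 hypoglycemic episode with SMBG value", gives the range 3.0 to <3.9 mmol/L (Level 1), and ends "was recorded, insulin dose should not be changed". It does not mention the median.
- The text above the table reads "In case of recorded hypoglycemic episodes any time during the period included in the assessment, the criteria provided as footnotes to" that table, and says these criteria are to be followed.

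Section 6.5.2 item 1 opens with a condition, "If increased risk of hypoglycemia during the period between 2 insulin dose assessments is judged to be related to the treatment regimen". It then instructs: "Decrease the insulin glargine dose by 2 U, per the TTT algorithm, in the following cases". Its list repeats the two triggers in footnote b and adds a third, joined by and/or: "If the median FPG value for the assessment period is <4.4 mmol/L". It does not repeat footnote c.

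**The concern.** When the median is <4.4 mmol/L and exactly one Level 1 episode was recorded, the row says to reduce and the footnote on the same cell says to leave the dose alone. Section 6.5.2 sides with the row. Taken at its word, the footnote makes the rule run backwards: the recorded low value is what stops the reduction.

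This is the low-glucose end of an insulin rule that participants apply themselves each week in the titration period. Hypoglycemic episodes and percentage change in glargine dose are both secondary endpoints. Compliance with the algorithm is recorded in the eCRF, and in this case either action could be scored as compliant, depending on how the footnote is read.

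**Working it through.** The plan gives no figure here to reproduce. The check has three parts.

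**1. The rules side by side, median <4.4 mmol/L.** The table is read literally, with footnotes followed when an episode is recorded. Section 6.5.2 is read with its opening judgment already made.

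| Recorded episodes | Table GPIM.1, literal | Section 6.5.2 |
|---|---|---|
| None | -2 | -2 |
| Exactly one, 3.0 to <3.9 | 0 | -2 |
| Two or more nonsevere | -2 | -2 |
| Any <3.0 or severe | -2 | -2 |

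The literal table goes -2, 0, -2 for zero, one and two Level 1 episodes. This reversal lies inside the table and does not depend on Section 6.5.2.

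**2. Can the case occur?** Yes. Fasting values 3.7, 4.2, 4.3 have median 4.2 and one Level 1 value. Footnote c gives no change; the row gives -2. Replace 3.7 by 3.9: the median is still 4.2, there is no episode, and the table gives -2. With three values, a median <3.9 means at least two values <3.9, so footnote b already gives -2. The disputed zone is therefore a median of 3.9 to <4.4 mmol/L.

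**3. How often?** The documents give no glucose variability, so the inputs are assumed: seven independent normal fasting values per week, rounded to 0.1 mmol/L. A week is in dispute if the median of the last three is <4.4, exactly one of the seven values is 3.0 to <3.9, and none is <3.0. Each cell shows the share of assessments with median <4.4, then the share of all weekly assessments.

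| Mean | SD 0.5 | SD 0.7 | SD 0.9 |
|---|---|---|---|
| 4.2 | 28% / 19% | 16% / 10% | 9% / 6% |
| 4.5 | 41% / 13% | 31% / 12% | 20% / 8% |
| 4.8 | 31% / 3% | 40% / 7% | 31% / 7% |
| 5.1 | 20% / 0.2-0.3% | 40% / 2.2% | 38% / 4% |

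The second figure is the first times the chance of a median <4.4. At mean 5.1 and SD 0.7 that chance is about 5.5%, and 0.055 × 0.40 = 2.2%. At mean 5.6, the upper edge of the protocol's fasting target, the share of all assessments is at most 0.8% for SD 0.5 to 0.9.

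The disputed step is 2 U. Against the 15 U/day figure in inclusion criterion 4 that is 2/15 = 13%; at higher doses it is a smaller fraction.

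**The case against.** The best defense is that footnote c is a companion to footnote b. Footnote b says the dose should also be decreased for certain episodes, so it adds to the row. Footnote c then marks the lower limit: one Level 1 episode is not by itself a reason to reduce. On that reading the row still gives -2 units, the table agrees with Section 6.5.2, and the reversal disappears. This is plausible and may be what was meant. But the text does not say it, the marker sits on the very cell that the footnote would leave untouched, and the sentence above the table directs the reader to the footnotes.

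A reader might infer that Section 6.5.2 flatly orders the opposite of the table. That is too strong. Its list applies only after a judgment that the risk is related to the regimen, and it acts through the same algorithm, so it points back to the table.

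Safeguards also count. Participants are to contact the site if they cannot decide, and staff verify adjustments at each office or telephone visit. The diary and training material may word the case clearly, but they are not among the documents. In the lead-in and stabilization periods, Section 4.1.1 limits adjustments to listed safety events, and this case is not one of them. These points limit the effect. They do not settle the wording: footnote c looks like a definite answer and so need not prompt a call, and after Week 16 office visits are 4 to 8 weeks apart while assessments stay weekly.

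**Conclusion.** The inconsistency is real on the literal reading of Table GPIM.1, and nothing in the protocol rules that reading out. It arises mainly in the 36-week unrestricted titration period and concerns one 2-unit step per weekly assessment.

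Its frequency cannot be known from the documents. The 9-41% figure describes only assessments already below 4.4 mmol/L. Over the same assumed grid the case makes up about 0.3-19% of all weekly assessments, and under 1% at mean 5.6. The figures rest on independence between days and count fasting lows only, whereas the hypoglycemia criteria in the footnotes cover the whole day; daytime episodes could move cases in or out.

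A reader might go further and infer harm to participants or a biased HbA1c comparison. The documents support neither. The same algorithm applies to all four double-blind arms, and the two endpoints named are additional secondary endpoints outside type 1 error control. This is a should-fix clarification of a safety rule, not a threat to the primary result.

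**What to change.** Reconcile four places so that one instruction applies when the median is <4.4 mmol/L and exactly one episode of 3.0 to <3.9 mmol/L was recorded: the <4.4 row of Table GPIM.1, footnote c, the Section 6.1.3 sentence on following the footnotes, and Section 6.5.2 item 1. State in footnote c which rows it governs, including whether it bears on the rows that raise the dose. Carry the same wording into the participant diary, the training material and the algorithm-compliance check. Which instruction applies is for the sponsor's clinical team to decide.

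The cost is a short protocol clarification and matching edits to diary and training text, with no added visits, procedures or participants.
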